## **8.2. Planned Analyses**

### **8.2.1. Interim Analysis**

Before the final analysis, interim analyses may be conducted, and the analyses may be submitted to regulatory agencies to seek guidance for the overall clinical development program. Also, interim analyses may be used for publication and/or presentation at scientific meetings.

#### **8.2.1.1. Dose Confirmation Analysis**

There will be 2 planned SRT meetings in this study.

The first SRT will confirm the ODV doses being used in Cohort 1 Part A after review of safety and available PK data from approximately 24 participants from Cohort 1 Part A who have completed at least Day 5 assessments or prematurely discontinued from the study. In addition, the first SRT will also confirm the ODV doses to be evaluated in Cohort 2 and Cohort 1 Part B.

The second SRT will confirm the ODV doses being used in Cohort 2 (and Cohort 1 Part B, if data are available) after review of safety and available PK data from approximately 12 participants from Cohort 2 who have completed at least Day 5 assessments or prematurely discontinued from the study.

Further details will be provided in the SRT charter.

#### **8.2.1.2. Data Monitoring Committee Analysis**

There will be 2 planned DMC meetings in this study.

An external DMC will review the progress of the study and perform interim review(s) of safety and available PK data.

The first DMC meeting will be conducted after approximately 24 participants in Cohort 1 Part A have completed at least their Day 5 assessments or prematurely discontinued from the study. This meeting will also confirm the initiation of Cohort 2 and Cohort 1 Part B.

The second DMC meeting will be conducted after approximately 12 participants in Cohort 2 have completed at least their Day 5 assessments or prematurely discontinued from the study.

The DMC membership, activities, and meeting schedule will be defined in a DMC charter. No formal stopping rules will be used by the DMC for safety outcomes. A clinical assessment will instead be made to determine if the nature, frequency, and severity of AEs associated with a study drug regimen warrant the early termination of the study in the best interest of the participants.

### 8.2.2. Final Analysis

The unblinded final analysis will be performed after all participants have completed the study, outstanding data queries have been resolved or adjudicated as unresolvable, and the data have been cleaned and finalized.

## 8.3. Analysis Conventions

### 8.3.1. Analysis Sets

The analysis sets are defined in [Table 5](#).

**Table 5. Analysis Set Definitions**

Analysis Set	Description
FAS	The FAS will include all participants who (1) are randomized into the study and (2) have received at least 1 dose of study drug. Participants will be grouped according to the treatment to which they were randomized.
FAPS	The primary analysis set for efficacy analyses is defined as all participants who (1) are randomized into the study, (2) have received at least 1 dose of study drug, (3) are RSV positive at baseline by a central laboratory test. Participants will be grouped according to the treatment to which they were randomized.
Safety Analysis Set	The primary analysis set for safety analyses is defined as all participants who (1) are randomized into the study and (2) have received at least 1 dose of study drug. Participants will be grouped according to the treatment they received.
Virology Analysis Set	The Virology Analysis Set will include all participants who (1) are randomized into the study, (2) have received at least 1 dose of study drug, and (3) have a baseline RSV viral load greater than or equal to the LLOQ. Participants will be grouped according to the treatment they received.

Analysis Set	Description
PK Analysis Set	The PK Analysis Set will include all participants who (1) are randomized in the study, (2) have received $\geq 1$ dose of study drug, and (3) have $\geq 1$ nonmissing result for PK evaluation of GS-441524. Participants will be grouped according to the treatment they received.

FAPS = Full Analysis Positive Set; FAS = Full Analysis Set; LLOQ = lower limit of quantitation; PK = pharmacokinetic(s); RSV = respiratory syncytial virus

### 8.3.2. Data Handling Conventions

Natural logarithm transformation for PK parameters will be applied for PK analysis.

For summary statistics, PK concentration values below the limit of quantitation will be treated as zero at predose and one-half of the lower limit of quantitation (LLOQ) for postdose time points.

Laboratory data that are continuous in nature but are less than the LLOQ or above the upper limit of quantitation, will be imputed to the value of the lower or upper limit plus or minus 1 significant digit, respectively (eg, if the result of a continuous laboratory test is  $< 20$ , a value of 19 will be assigned).

Missing data can have an impact upon the interpretation of the study data. In general, values for missing data will not be imputed. However, a missing pretreatment laboratory result would be treated as normal (ie, no toxicity grade) for the laboratory abnormality summary.

All available data for participants that do not complete the study will be included in data listings.

### 8.4. Demographic and Baseline Characteristics Analysis

Demographic and baseline measurements will be summarized using standard descriptive methods.

Demographic summaries will include sex, race/ethnicity, and age.

Baseline data will include a summary of body weight, height, and body mass index.

No formal statistical testing is planned.

### 8.5. Efficacy Analysis

For all efficacy analyses, the Full Analysis Positive Set (Section 8.3.1) will be used, unless otherwise specified. No formal statistical testing is planned.

#### 8.5.1. Primary Analysis

The analysis of the primary efficacy endpoint will be based on the primary estimand outlined in Table 6.

**Table 6. Primary Estimand for Primary Efficacy Endpoint**

Attribute	Details
Target population	Study population as defined by protocol eligibility criteria
Treatment condition(s)	ODV and placebo, regardless of treatment discontinuation/modification, RSV-related hospitalization, or RSV-related MAVs
Variable	Time (days) to alleviation of targeted RSV symptoms by Day 28 in the absence of rescue medication and all-cause death
Handling of ICEs	
The following scenarios if they occur prior to alleviation of targeted RSV symptoms by Day 28 will be considered:
 
 
• Treatment discontinuation/modification: treatment policy (included as part of the treatment condition(s) attribute)
 
• Use of rescue medication: composite strategy (included as part of the variable attribute). Note: details on the applicable rescue medications will be provided in the SAP
 
• All-cause death: composite strategy (included as part of the variable attribute)
 
• RSV-related hospitalization: treatment policy (included as part of the treatment condition(s) attribute)
 
• RSV-related MAVs: treatment policy (included as part of the treatment condition(s) attribute)
 

Population-level summary	Difference in median variable (as defined in the variable attribute) between ODV and placebo

ICE = intercurrent events; MAV = medically attended visit; ODV = obeldesivir; RSV = respiratory syncytial virus; SAP = statistical analysis plan

The estimate of the primary estimand is the difference in median time (days) to alleviation of targeted RSV symptoms by Day 28 in the absence of rescue medication and all-cause death between ODV and placebo as defined by protocol eligibility criteria. This will be estimated regardless of treatment discontinuation/modification, RSV-related hospitalization, or RSV-related MAVs (ie, treatment policy).

The time to alleviation of targeted RSV symptoms by Day 28 is calculated as the symptom alleviation date minus the first dose date. In case, prior to data cutoff a participant:

- Completes the study without alleviation of targeted RSV symptoms
- Prematurely discontinues from the study prior to alleviation of targeted RSV symptoms (due to AE, lack of efficacy, investigator's discretion, noncompliance with study drug, protocol violation, participant decision, lost to follow-up)

The time to sustained alleviation of targeted RSV symptoms will be calculated as the last date on which the symptom alleviation is assessed minus the first dose date or Day 27, whichever occurs first.

If a participant takes rescue medication or dies prior to alleviation of targeted RSV symptoms (ie, composite strategy) the participant will be censored at the last date on which symptom alleviation is assessed prior to the start of rescue medication or death.

The median time (days) to symptom alleviation along with the associated 95% CI will be estimated by treatment group using the Kaplan-Meier (KM) method. A log-rank test will be used to compare the treatment difference in time to alleviation of targeted RSV symptoms between ODV and placebo. The proportion of participants with alleviation of targeted RSV symptoms using KM estimates will be provided in tables and plots by treatment group.

Furthermore, to support the analysis of the primary efficacy endpoint, a Cox proportional hazards regression model will be used to estimate the hazard ratio and corresponding 95% CI.

Sensitivity analysis associated with the primary endpoint may be performed:

- A nonparametric analysis where the median time (days) to symptom alleviation of targeted RSV symptoms along with the associated 95% CI will be estimated by treatment group using the methodology of Hodges-Lehmann.
- Missing targeted RSV symptom alleviation status will be imputed using multiple imputation assuming missing at random.
- Restricted mean time to alleviation of targeted RSV symptoms will be provided by treatment group.

Subgroup analysis of the primary efficacy endpoint will be performed to investigate the impact of important demographic and other baseline characteristics (eg, cohort, sex, race, risk factors for severe RSV disease). In addition, if important respiratory coinfections are identified at Day 1, a further subgroup analysis of the primary efficacy endpoint to assess the impact of respiratory coinfections will be performed. More details on subgroup analyses will be provided in the SAP.

The number and percentage of participants experiencing an intercurrent event by treatment group will also be provided.

### **8.5.2. Secondary Analyses**

The estimand for time to sustained alleviation of targeted RSV symptoms by Day 28 is the difference in median time (days) to sustained alleviation of targeted RSV symptoms in the absence of rescue medication and all-cause death between ODV and placebo in the study population. This will be estimated regardless of treatment discontinuation/modification, RSV-related hospitalization, or RSV-related MAVs. Similar analyses as outlined in Section 8.5.1 will be performed.

The estimand for time to resolution of targeted RSV symptoms by Day 28 is the difference in median time (days) to resolution of targeted RSV symptoms in the absence of rescue medication and all-cause death between ODV and placebo in the study population. This will be estimated

regardless of treatment discontinuation/modification, RSV-related hospitalization, or RSV-related MAVs. Similar analyses as outlined in Section 8.5.1 will be performed.

Analysis of virology data will be conducted in the Virology Analysis Set (Section 8.3.1). The estimand for change from baseline in RSV nasal swab viral load at Day 5 is the difference in least square means of change from baseline in RSV nasal swab viral load at Day 5 in the absence of rescue medication and all-cause death between ODV and placebo in the study population. This will be estimated regardless of treatment discontinuation/modification, RSV-related hospitalization, or RSV-related MAVs. The difference in change from baseline in RSV nasal swab viral load at Day 5 between ODV and placebo along with the associated 95% CI will be constructed using a mixed-effects model for repeated measures, including baseline RSV nasal swab viral load as a covariate and treatment group (ODV vs placebo), visit, and treatment group-by-visit interaction as fixed effects. The change from baseline in RSV nasal swab viral load at Day 5 will also be summarized by treatment group using descriptive statistics.

### **8.5.3. Adjustments for Multiplicity**

No adjustments for multiplicity are planned for this study as the primary efficacy evaluation is exploratory in nature. Nominal 95% CIs and tests performed at the nominal 0.05 alpha level will be provided.

## **8.6. Safety Analysis**

Analysis of safety data will be conducted in the Safety Analysis Set (Section 8.3.1). The treatment-emergent period is defined as the time period from the first dose of study drug to the earlier of 30 days after the last dose of study drug. All safety data during the treatment-emergent period will be summarized by treatment group (according to the study drug received). Data for the pretreatment and treatment-free periods will be included in data listings.

The safety variables to be analyzed include exposure to study treatment, AEs, deaths, clinical laboratory test results (hematology and chemistry), and vital sign measurements. Categorical safety data, including the primary safety endpoints associated with the number and percentage of participants with AEs and categorizations of laboratory test data, will be summarized using frequencies and percentages. Continuous safety data, including laboratory test data, will be summarized using descriptive statistics (n, mean, median, SD, SE, and range). No formal statistical testing is planned.

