## 8. STATISTICAL CONSIDERATIONS

This section provides a high-level description of the planned analyses, assessed statistical power with assumptions, and any applicable multiplicity adjustments. Additional details of the statistical methods will be provided in the statistical analysis plan (SAP), including any deviations from the original statistical analyses planned.

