	4		≥ 3 to < 6	50 mg twice on Day 1 and 30 mg twice daily on Days 2 to 5
CCI	I			

CA = chronological age; GA = gestational age; ODV = obeldesivir; PMA = postmenstrual age; SRT = safety review team
a Participants receiving only 1 of 2 doses on Day 1 will need to take their last dose on Day 6.
b The SRT will confirm the ODV doses to be evaluated in Cohort 2 and Cohort 1 Part B from the specified dose ranges.

The study treatment period was 5 days with a posttreatment follow-up period of up to 30 days after the last dose of study drug. For the entire duration of the study, participants and investigators remained blinded to the initial treatment regimen.

The timing of efficacy, PK, and safety assessments are presented in Appendix 1 and Appendix 2.

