3.2. Participant Grouping

For all analyses, participants will be grouped according to the cohort/weight group to which participants were randomized.

For analyses based on the All Randomized Analysis Set, FAS, FAPS, and Virology Analysis Set, participants will be grouped according to the treatment to which they were randomized. For analyses based on the Safety Analysis Set, participants will be grouped according to the actual treatment received. The actual treatment received will differ from the randomized treatment only when their actual treatment differs from randomized treatment for the entire treatment duration.

For the PK Analysis Set, participants will be grouped according to the actual treatment they received.

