7. SAFETY ANALYSES

Analysis of safety data will be conducted on the Safety Analysis Set, unless otherwise specified in the following sections. The treatment-emergent (TE) period is defined as the time period from the first dose date of study treatment up to and including 30 days after the last dose of study treatment.

All safety data during the TE period will be summarized by treatment group as defined in Section 3.2. Data for the pretreatment and treatment-free follow-up periods will be included in data listings.

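### For the safety tables, SAP 3.2 keeps a placebo-randomized child who took obeldesivir for part of the course under placebo; the protocol has no mixed-exposure rule, and the SAP fills the gap in a non-conservative way

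*Protocol*

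**What the plan says.** Protocol 8.6: "All safety data during the treatment-emergent period will be summarized by treatment group (according to the study drug received". Protocol Table 5 gives the same principle for the Safety Analysis Set: "Participants will be grouped according to the treatment they received". Neither place says how to classify a child who received both products. Protocol 8 leaves room for the SAP to do so: "Additional details of the statistical methods will be provided in the statistical analysis plan (SAP".

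SAP 3.2 begins from the same principle: "For analyses based on the Safety Analysis Set, participants will be grouped according to the actual treatment received". The next sentence defines it: "The actual treatment received will differ from the randomized treatment only when their actual treatment differs from randomized treatment for the entire treatment duration". SAP 7 carries that definition into every safety summary: "All safety data during the TE period will be summarized by treatment group as defined in Section 3.2". The changes declared in SAP 2.3 and 7.7 do not mention grouping.

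On exposure, SAP 1.2 states: "The study treatment period was 5 days with a posttreatment follow-up period of up to 30 days". Dosing is twice daily, and the procedures table shows one dispensation, on Day 1.

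**The concern.** An as-received safety analysis is meant to place events with the product to which the child was exposed. The SAP definition achieves this only when the wrong product was taken throughout. For any mixture it returns the randomized arm. A placebo-randomized child who took ODV for most of the course, and then had an adverse event or a Grade 3 or 4 laboratory abnormality, would be reported as a placebo child with an event.

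Both proportions, by Day 28, are primary endpoints (Protocol 2, SAP 1.1). Such a case would raise the control rate and take an event out of the ODV column. That is the unwelcome direction for a safety table. The study stopped early, and SAP 6.3 describes the number enrolled as limited, so one child carries weight. SAP 7.1.6 and 7.2.1.2 also tabulate these outcomes within each cohort/weight group, where the denominators are smaller still.

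**Working it through.** **Inputs.** Treatment period 5 days (SAP 1.2). Two doses a day (Protocol Table 1, footnote p; SAP Appendix 1, footnote p). Planned size at least 130, allocated 2:1 (SAP 1.2). Enrolled number: not given. The plan states no figure on this point to reproduce.

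**Step 1: doses affected.** Scheduled doses = 5 × 2 = 10. Under SAP 3.2 a child changes column only at 10 of 10 wrong doses. From 1 to 9 wrong doses (10% to 90% of the course), the child stays as randomized.

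**Step 2: where the SAP rule and an any-ODV-dose rule differ.**

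| Randomized to | Actually took | SAP 3.2 | Any-ODV-dose rule |
|---|---|---|---|
| ODV | both products | ODV | ODV |
| ODV | placebo only, whole course | placebo | placebo |
| Placebo | ODV only, whole course | ODV | ODV |
| Placebo | both products | **placebo** | **ODV** |

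The SAP wording is symmetric, but the two rules part in one row only. Relative to the any-dose rule, SAP 3.2 can move an ODV-exposed child into placebo and never the reverse.

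**Step 3: weight of one child.** Let n be the number in the placebo column, counting the misplaced child, and x the number of other placebo children with an event. If the misplaced child has an event:

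- placebo rate under SAP 3.2: (x + 1)/n
- placebo rate with the child removed: x/(n − 1)
- difference: (1/n) × [1 − x/(n − 1)], which is at most 1/n, reached when x = 0.

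Maximum shift, 100/n percentage points:

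- n = 10 (assumed): 100/10 = 10 points
- n = 5 (assumed): 100/5 = 20 points
- for reference, the planned placebo arm of 130/3 ≈ 43: 100/43 = 2.3 points; that size was not reached.

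The shift is smaller when other placebo children also have events. For n = 5 and x = 2, it is 3/5 − 2/4 = 60% − 50% = 10 points. If the misplaced child has no event, the placebo rate falls slightly instead, by x/[n(n − 1)].

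**Step 4: would the listings show it?** SAP 3 puts the randomized treatment group in the listings, so the adverse event listing would also label this child placebo. The mixture would have to be found in the dosing and accountability listing (SAP 4.2.1) or the protocol deviation listing (SAP 4.3).

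**The case against.** The strongest reply is that the case hardly arises. Drug is dispensed once for a 5-day course, so a wrong kit would usually mean the wrong product throughout, which SAP 3.2 does reclassify. If the error comes to light by disclosing the assignment to the investigator, Protocol 5.1.4 has treatment discontinued, and the child may then have taken only one product. Only the placebo third can be affected. Safety is descriptive, and in a small terminated study one child can be traced through the listings. All of this lowers the weight of the point. It does not make the rule sound: Protocol 7.1.4 itself provides for dispensing and administration errors, and caregivers may record doses.

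An any-dose rule also has a price. One mistaken ODV dose puts all of that child's treatment-emergent events under ODV. That is true, but for a safety table it is the more cautious side on which to err.

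Three stronger readings are tempting and are not supported:

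- *That the SAP contradicts the protocol.* The protocol has no any-dose or majority rule, such a child did receive both products, and method detail is left to the SAP. This is a gap filled in a non-conservative way, so the absence of an entry in SAP 7.7 is not an undeclared change.
- *That ODV-exposed children's drug concentrations would appear under placebo.* The PK rule is a separate paragraph without the qualifier: "For the PK Analysis Set, participants will be grouped according to the actual treatment they received". SAP 8.2 summarizes concentrations by cohort/weight group and specifies no placebo column.
- *That the effect can be sized from the planned Cohort 2.* That cohort was to open after safety and data monitoring reviews which, according to SAP 1.2, were not conducted.

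**Conclusion.** The point holds as a minor weakness in SAP 3.2. For the Safety Analysis Set, a placebo-randomized child with partial ODV exposure is counted as placebo, and an event after ODV exposure can be reported as a placebo event on a primary endpoint. The size is conditional: up to 10 to 20 percentage points on the placebo rate for one such child with an event, assuming 5 to 10 children in the placebo column and no events among the others. It is zero if no child had mixed exposure, and nothing in the documents shows that one did.

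**What to change.** In SAP 3.2, for the Safety Analysis Set only, replace the sentence on the entire treatment duration with: *a participant who took at least 1 dose of ODV is analysed as ODV; a participant who took only placebo is analysed as placebo.* Flag any mixed-exposure child in the study drug administration and adverse event listings.

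Settle this before unblinding, so that the choice cannot look data-driven; SAP 3.1 already fixes analysis-set membership before the blind is broken. If the SAP is final, SAP 1 provides for recording the change in the clinical study report.

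The cost is one sentence and one derivation from dosing data already collected, plus the slight dilution of the ODV column by a child with a single mistaken dose, which the flag makes visible. If the sponsor prefers to keep the current rule, the minimum is a footnote to the safety tables and a separate listing of such children's events.

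Separately, Protocol Table 5 groups the Virology Analysis Set by treatment received and SAP 3.2 groups it as randomized. The two should be reconciled, but this fix does not depend on it.
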